## 7.2 General Methodology

The study will be considered successful when the primary objective is met. To support an indication for OAB, device therapy effectiveness will be demonstrated for the symptoms associated with OAB, including UUI, UF, and urgency.

For each of the objectives, the available data will be summarized, and missing data will be discussed. The main analysis of the study objectives will be intention-to-treat, meaning that the analysis will use the Full Analysis Set (FAS). The FAS includes all subjects, using the intention-to-treat (ITT) principle, who have an attempted device implant. Additional information on missing data plans are found in section 7.4.

Analyses of all data will be summarized with standard descriptive summary statistics, including counts and percentages for categorical variables, and mean, standard deviation, median, minimum, and maximum for continuous variables. The primary objective will be tested as described in section 7.9.1.1. If the primary objective is passed, the secondary objectives will each be tested as described in section 7.9.2 following the Hochberg multiple testing strategy. All p-values will be reported as 2-sided tests. Additionally, 95% Confidence intervals will be supplied for selected measures.

Safety data will be summarized as the count of events, count of subjects, and percentage of subjects who experienced the event. Subject disposition will be illustrated in a flow diagram. Subject visits will be tabulated and compliance to the visit schedule and visit windows will be summarized. Attrition will be identified and summarized, including the number and causes of death if any occur in the study.

Data analysis will be performed by Medtronic-employed statisticians or designees. A validated statistical software package (e.g., SAS version 9.4 or higher) will be used to analyze the study results. PASS 2019 sample size calculation software was utilized for determination of sample sizes and associated statistical power calculations.

### 7.2.1 Justification of study design

The single-arm nature of the study design has a limitation of no randomized concurrent control group. However, due to therapy sensations delivered by TNM, no blinded study design is possible. Without blinding, expectation differences may result in widespread placebo effect differences between the active and control therapies, which may introduce group differences that are not due to treatment. Instead, the use of a performance goal defines a specific relevant effect that must be overcome to identify a successful therapy.

### 7.2.2 Diary Data Analysis

Several objectives [REDACTED] are based on the analysis of voiding diary data. The diary will be collected for 3 days prior to or after each study visit. The center will assign each diary to the corresponding visit in the eCRF. In some cases, the diary might be completed for slightly less or more than 3 days (e.g., for 68 or 75 rather than the expected 72 hours). All diaries which are greater than 48

hours will be used for analysis. For UI, UUI, and UF, the total number of episodes will be determined for each subject's diary collection period at each visit. UUI episodes are those leaks with urgency greater than none, urinary incontinence (UI) episodes are all leaks, and UF are all voiding episodes. The actual total length of the diary for each visit will be determined by using the subject-specific diary start and end time reported by the center. The number of episodes will be divided by the total length of the diary for that subject at the visit and reported as a daily (24 hour) rate (i.e., 'per day'). The change will be determined by subtracting the baseline value per day from the follow-up value per day. Percentage change will be determined by dividing the change in episodes per day by the baseline value. Negative values for change and percentage change represent an improvement. Responder rate for UUI is defined as the proportion of TNM subjects experiencing a reduction of 50% or more in daily UUI episodes. Responder rate for UF is defined as the proportion of TNM subjects experiencing a reduction of 50% or more in daily UF episodes or a return of voiding to <8 voids per day. Responder rate for UI is defined as the proportion of TNM subjects experiencing a reduction of 50% or more in daily UI episodes. Responder rate for UU is defined as the proportion of TNM subjects with an improvement of at least 1 point on the UPS. OAB responder rate is defined as the proportion of TNM subjects who are considered either a UUI, UF, or UU responder.

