14.1.5 Diary Data Analysis

The primary and several other objectives and additional measures are based on the analysis of voiding diary data. The diary will be collected for 3 days prior to or after each study visit. The site will assign each diary to the corresponding visit in the eCRF. In some cases, the diary might be completed for slightly less or more than 3 days (e.g., for 68 or 75 rather than the expected 72 hours). All diaries which are greater than 48 hours will be used for analysis. For UI, UUI, and UF, the total number of episodes will be determined for each subject's diary collection period at each visit. The actual total length of the diary for each visit will be determined by using the subject-specific diary start and end time reported by the site. The number of episodes will be divided by the total length of the diary for that subject at the visit and reported as a daily (24 hour) rate (i.e., 'per day'). The change will be determined by subtracting the baseline value per day from the follow-up value per day. Percentage change will be determined by dividing the change in episodes per day by the baseline value. Negative values for change and percentage change represent an improvement. Responder rate for UUI is defined as the proportion of TNM subjects experiencing a reduction of 50% or more in daily urinary urge incontinence (UUI) episodes. Responder rate for UF is defined as the proportion of TNM subjects experiencing a reduction of 50% or more in daily urinary frequency (UF) episodes or a return of voiding to <8 voids per day. Responder rate for UI is defined as the proportion of TNM subjects experiencing a reduction of 50% or more in daily urinary incontinence (UI) episodes. Responder rate for urinary urgency (UU) is defined as the proportion of TNM subjects with an improvement of at least 1 point on the UPS. OAB responder rate is defined as the proportion of TNM subjects who are considered either a UUI, UF, or UU responder.

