## **7.4 Handling of Missing, Unused, and Spurious Data and Dropouts**

Primary and secondary objectives will be analyzed using the FAS. The FAS includes all subjects, using the intention-to-treat principle, who have an attempted device implant. All attempts will be made to minimize missing data. For diary-based metrics, missing is defined as any diary which has a total length of less than 48 hours, as defined in section 7.2.2. The OAB-q may be missing if the HRQL Total cannot be calculated; scoring details are found in section 7.9.2.4. If 5% of the data or fewer are missing for the analysis, no imputation will be used, and the data will be analyzed using the Complete Case analysis set (Buhi 2008). Otherwise, if missing data are observed, imputation will be used for the primary and secondary objectives.

The primary objective imputation will be done using multiple imputation (MI). Predictive mean matching multiple imputation will be used for each variable. First, multiple imputation will be applied to impute missing values in average daily UUI episodes. Unless model errors dictate otherwise, each model will consider Baseline and Month 1, Month 2, Month 3, and Month 6 variables for the UUI episodes variable and demographic variables of age, gender, history of pregnancy, and BMI. The fully conditional specification (FCS) method within SAS (version 9.4 or higher) with 30 repetitions and 100 burn-in iterations will be used for imputation. No limits will be defined for imputed values. Following

imputation, the 6-month outcome data will be converted to the appropriate endpoint (i.e., change from baseline/UUI responder). The estimate and variance of the mean proportion of subjects considered a UUI responder will be determined for each imputation dataset. For the primary objective, the mean and variance for the proportion will be determined using MI analysis methods and the objective will be tested using a Z-test comparing the observed responder rate to the primary objective performance goal of 40%.

For the UUI, UF, and OAB-Q secondary objectives, the following imputation steps will be taken:

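### The diary rate divides by elapsed start-to-end time, so a blank day inside the diary counts as episode-free; the primary test could be biased toward success if blank time is more common at month 6 than at baseline

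*SAP*

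**What the plan says.** SAP 7.2.2 and protocol 14.1.5 derive the UUI, UI and UF rates in the same way. The denominator is elapsed time: "The actual total length of the diary for each visit will be determined by using the subject-specific diary start and end time", as reported by the site. Then "The number of episodes will be divided by the total length of the diary for that subject at the visit", scaled to 24 hours. A UUI responder has a fall of at least 50% in this rate from baseline to month 6.

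The only completeness test uses the same elapsed length. Protocol 14.1.5 states: "All diaries which are greater than 48 hours will be used for analysis". SAP 7.4 states: "missing is defined as any diary which has a total length of less than 48 hours", and protocol 14.1.2 agrees. Neither document has a rule for blank hours, or a blank day, between start and end.

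The numerator rule in SAP 7.2.2 is "UUI episodes are those leaks with urgency greater than none". Nothing is said about a leak with no urgency score.

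The diaries are on paper (protocol 10.9 and 10.12). Sites review them for completeness, and staff may add only entries that the subject confirms.

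**The concern.** A blank day inside the span adds 24 hours to the denominator and nothing to the numerator, so unrecorded time is scored as time without episodes. Because the diary still passes the length check, it is not missing. It does not count toward the 5% trigger for imputation, and it stays in the complete-case set. None of the sensitivity analyses listed in SAP 7.9.1.1 is described as addressing it. The OAB-q, by contrast, has an item-level missing-data rule (SAP 7.9.2.4).

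The primary endpoint and the UUI and UF change endpoints all rest on this rate. The study succeeds or fails on the primary objective alone, in a single-arm design with no control group in which the same measurement error would appear.

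**Working it through.** **Inputs from the documents.** Performance goal 40%, alternative 55%, one-sided alpha 0.025, n = 121 (SAP 6); responder threshold 50% and expected diary length 72 h (SAP 7.2.2).

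**The plan's own figure.** The smallest r with P(X ≥ r | 121, 0.40) ≤ 0.025 is r = 60 (60/121 = 49.6%). Exact size is 0.0204 and power at 55% is 0.901. The stated power of at least 90% reproduces.

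**Effect on one subject.** Let f be the blank share of the reported span, so that computed rate = true rate × (1 − f).

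- Blank at month 6 only: a true reduction of 1 − 0.5/(1 − f) scores as 50%. For 24 h in 72 h, f = 1/3 and 1 − 0.5/(2/3) = 25.0%.
- Blank at baseline only: the true reduction needed is 1 − 0.5 × (1 − f) = 1 − 0.5 × 2/3 = 66.7%.
- Part-day gaps at month 6: 6 h (f = 0.083) gives 45.5%; 12 h (f = 0.167) gives 40.0%.

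Example: baseline 9 leaks in 72 h, or 3.0 per day. The month-6 diary spans 72 h with 24 h blank and has 4 leaks in the other 48 h. As written: 4/72 × 24 = 1.33 per day, a 55.6% reduction, responder. On recorded time: 4/48 × 24 = 2.0 per day, a 33.3% reduction, non-responder.

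**Effect on the primary test.** Assumptions, not in the documents: the true month-6/baseline ratio is lognormal with log SD 0.6, 0.85 or 1.1, set so that P(ratio ≤ 0.5) = 0.40; each affected diary has one blank day in 72 h; gaps at the two visits are independent. Then:

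- P(ratio ≤ 0.75), the chance of scoring as a responder with a blank month-6 day, is 0.66, 0.59 or 0.55.
- P(ratio ≤ 1/3), the same with a blank baseline day, is 0.18, 0.23 or 0.27.

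With shares a (month 6) and b (baseline) of diaries affected, the scored rate is a(1 − b) × P(≤ 0.75) + (1 − a)b × P(≤ 1/3) + [ab + (1 − a)(1 − b)] × 0.40. False success is P(X ≥ 60 | 121, scored rate).

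| Month 6 | Baseline | Scored rate | False success |
|---|---|---|---|
| 0% | 0% | 40.0% | 2.0% |
| 5% | 0% | 40.7-41.3% | 3.0-4.0% |
| 10% | 0% | 41.5-42.6% | 4.3-7.4% |
| 20% | 0% | 42.9-45.3% | 8.3-19.4% |
| 20% | 10% | 41.6-43.0% | 4.5-8.4% |
| 5-20% | same | 40.1-40.6% | 2.1-2.9% |

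**Cross-check with another model.** A simulation with Poisson diary counts, a gamma baseline (mean 4 per day, SD 3), log SD 0.9 and at least 3 baseline episodes gave 4.5% and 8.9% for month-6 gaps in 10% and 20% of diaries. Dividing by recorded time brought these to 2.2% and 2.3%. Equal gaps at both visits in 10% and 20% gave 2.8% and 3.2%.

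**The 48-hour limit.** Usable means above 48 h and missing means below 48 h, so exactly 48 h is in neither class.

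**The case against.** The strongest reply is that the formula is the same at both visits. Gaps at baseline work against response, and equal gaps largely cancel, as the last row of the table shows. A reader might infer that the rule always favours the device; the documents do not support that. The baseline check requires at least 3 UUI episodes in 72 hours, which is a count and not a completeness check, and site review for completeness is not confined to baseline. An excess of gaps at month 6 is plausible, since diary training is given at baseline and the protocol lists diary burden as an example of a reason for withdrawal, but nothing in the documents establishes it.

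Second, the length is subject-specific, and 68 and 75 hours are given as examples. A blank first or last day may simply shorten the reported span. If blank days fall evenly over the three days and only the middle one stays in the denominator, month-6-only gaps in 5%, 10% or 20% of diaries give false success of 2.3-2.6%, 2.7-3.2% or 3.4-5.0%. For the same reason, one should not lead with two blank days, where a subject up to 50% worse would still score as a responder (0.5/(1/3) = 1.5): at least one of those days would have to lie at the edge and still be inside the reported span.

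Third, there are conduct safeguards: edit checks for missing data with site queries (protocol 16.2), source data verification (16.3), reminder calls (10.1) and subject-confirmed entries (10.12). They should reduce gaps, but they do not say how a remaining gap is scored.

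Finally, a reader might infer that leaks with a blank urgency score will drop out of UUI. That presumes one particular way of coding. The documents do not say how such leaks are handled, the primary-endpoint code gets Level I validation (SAP 8), and all-leak analyses are already planned. Counting those leaks as UUI would also raise baseline counts and make response easier, so this belongs in a sensitivity analysis.

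**Conclusion.** The concern stands as a conditional one. The stated rule gives a wrong rate whenever a whole blank day lies inside the reported span, and no missing-data rule catches it. The primary test could be biased toward success if blank time is more common at month 6 than at baseline. Under the lognormal assumption, false success lies between near the design value (equal gaps) and 8.4% (20% against 10%), and higher if gaps occur at month 6 alone and are frequent. If blank edge days shorten the span, the effect is smaller. The documents give no gap frequency, so the actual size and direction are unknown. The gap at exactly 48 hours is certain but minor by itself. This should be fixed before the data are analysed; it does not by itself invalidate the primary test.

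**What to change.** In SAP 7.2.2 and 7.4 and protocol 14.1.2 and 14.1.5:

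- Compute rates on recorded time at every visit: remove from the denominator any 24-hour diary day with no void or leak entry. All voids are recorded, so such days can be found in data already collected.
- Treat a diary with fewer than 48 recorded hours as missing, and define usable as 48 hours or more throughout. The boundary then matters, because a 72-hour diary with one blank day has exactly 48 recorded hours.
- Add a sensitivity analysis that counts leaks with a blank urgency score as UUI at every visit, alongside the planned all-leak (UI) analysis.

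The cost is wording and a few lines of derivation code. A few more diaries become missing (a 68-hour diary with a blank day keeps 44 hours), which may bring the imputation trigger nearer: 6/121 = 4.96% is within 5%, 7/121 = 5.8% is not. The responder rate may be slightly lower. Part-day gaps of the kind shown above remain.

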### 7.3 Center Pooling

The investigators of this study will conduct the study according to this protocol and use the study-specific eCRFs to collect study data. The study center personnel will be trained prior to the study initiation at each study center. Periodic study monitoring by Medtronic will ensure compliance with

protocol requirements. Therefore, there is no a priori provision to exclude any study centers from the analysis. The data from all study centers will be pooled for analysis. To reduce the possibility of atypical results from a study center overly influencing the combined results, no more than 24 subjects will be implanted at each study center. The per-study center enrollment cap may be increased upon Sponsor approval.

As an exploratory analysis to assess if treatment effect differs by study center, Freeman and Halton's extension of Fisher's exact test will be conducted using UUI responder as the response variable. This analysis will be based on the Complete Case analysis set for the primary objective. If the p-value approaches statistical significance (defined as  $\leq 0.15$ ), the percentage of subjects who are considered a UUI responder will be presented by center. If center(s) causing the significance are identified, variables relating to patient characteristics and other factors will be analyzed to try to identify why this center is showing a different treatment effect.

To increase the power of the test for treatment-by-center interaction, all study centers that are too small (fewer than four implanted subjects) to be reliably analyzed alone or to have a noticeable impact on overall study results will be combined into one "virtual" study center. All other study centers with four or more implanted subjects will stand alone in the analysis. If the virtual study center is larger than 30 implanted subjects (~25% of the required sample size), the virtual study center will be split into 2 virtual study centers defined by ordering the study centers alphabetically and splitting the study centers as near the midpoint as possible. In the case that the midpoint is within an individual study center, that study center will be included with the study centers from earlier in the alphabet.

## **7.4 Handling of Missing, Unused, and Spurious Data and Dropouts**

Primary and secondary objectives will be analyzed using the FAS. The FAS includes all subjects, using the intention-to-treat principle, who have an attempted device implant. All attempts will be made to minimize missing data. For diary-based metrics, missing is defined as any diary which has a total length of less than 48 hours, as defined in section 7.2.2. The OAB-q may be missing if the HRQL Total cannot be calculated; scoring details are found in section 7.9.2.4. If 5% of the data or fewer are missing for the analysis, no imputation will be used, and the data will be analyzed using the Complete Case analysis set (Buhi 2008). Otherwise, if missing data are observed, imputation will be used for the primary and secondary objectives.

The primary objective imputation will be done using multiple imputation (MI). Predictive mean matching multiple imputation will be used for each variable. First, multiple imputation will be applied to impute missing values in average daily UUI episodes. Unless model errors dictate otherwise, each model will consider Baseline and Month 1, Month 2, Month 3, and Month 6 variables for the UUI episodes variable and demographic variables of age, gender, history of pregnancy, and BMI. The fully conditional specification (FCS) method within SAS (version 9.4 or higher) with 30 repetitions and 100 burn-in iterations will be used for imputation. No limits will be defined for imputed values. Following

imputation, the 6-month outcome data will be converted to the appropriate endpoint (i.e., change from baseline/UUI responder). The estimate and variance of the mean proportion of subjects considered a UUI responder will be determined for each imputation dataset. For the primary objective, the mean and variance for the proportion will be determined using MI analysis methods and the objective will be tested using a Z-test comparing the observed responder rate to the primary objective performance goal of 40%.

For the UUI, UF, and OAB-Q secondary objectives, the following imputation steps will be taken:

- For secondary objectives related to UUI episodes, the imputation datasets created for the primary objective will be used. For OAB-q HRQL and UF episodes, a new set of imputation datasets will be created following the same methods as the primary objective but replacing UUI episodes with OAB-q HRQL or UF episodes. For OAB-q HRQL, the imputation model contains HRQL scores only at those visits where the assessment was collected (Baseline, Month 3, Month 6). Constraints will be set so that the imputed OAB-q HRQL are restricted to values ranging from 0-100. If the MI procedure is unable to successfully impute values within that range, the constraints will be applied after imputation, such that any values less than 0 will be set to 0, and any values greater than 100 will be set to 100.
- After imputation, the normality for the outcome metric will be checked through Shapiro-Wilk test for each imputation dataset. If  $p\text{-value} > 0.05$  for at least 15 imputed datasets (half of the total), it will be considered that the data are normally distributed. In this case, the mean and standard error of the outcome metric will be calculated within each imputed dataset, and then combined using MI analysis methods. The mean and standard error of the outcome metric will be reported, and the objective will be tested with a t-test.
- If the distribution of outcome metric is non-normal ( $p\text{-values} \leq 0.05$  in more than 15 of the imputed datasets), MI will not be used. Instead, last observations carried forward (LOCF) will be applied, with the imputed dataset tested using the Wilcoxon signed-rank test.

For the secondary objective related to urgency using the UPS, the imputation datasets will be created using multiple imputation (MI). Logistic regression multiple imputation will be used for each variable which accounts for the ordinal nature of the UPS. First, multiple imputation will be applied to impute missing values in UPS. Unless model errors dictate otherwise, each model will consider Baseline, Month 3, and Month 6 variables for the UPS variable and demographic variables of age, gender, history of pregnancy, and BMI. The fully conditional specification (FCS) method within SAS (version 9.4 or higher) with 30 repetitions and 100 burn-in iterations will be used for imputation. Imputed values will be required to be 1, 2, or 3 to match the original scale. After imputation, the mean and standard error of the change from Baseline to Month 6 in UPS will be calculated within each imputed dataset, and then combined using MI analysis methods. The mean and standard error will be reported, and the objective will be tested with a t-test.

Sensitivity analyses will be completed for the primary and secondary objectives including subjects who received a TNM implant (“All Implanted Analysis”), using only subjects with outcome data at baseline

and follow-up (“Complete Case Analysis”), and using only those complete case subjects who received stimulation (“As Treated Analysis”).

[REDACTED] Comprehensive descriptions of subject accountability and missing data will be provided.

